12. LIMITATIONS AND STRENGTHS

12.1 Limitations

There are some limitations in the protocol that need to be considered for future analysis and extrapolation of results.

Selection bias

The first potential source of bias relates to the **recruitment of the sample**. Consecutive sampling will be used, which is a non-probabilistic method. Therefore, there is a possibility of not obtaining the most representative population. In order to mitigate this selection bias and to ensure strong external validity, extensive inclusion criteria have been formulated, while exclusion criteria have been designed to reduce any confounding factors. We are aware that the sampled population may not mirror the general population. However, we consider that it is closer to the real target population that may benefit from the final results.

The second bias in the selection phase is the **participation rate**, as we assume that two years and two months of recruitment will be enough to achieve an ideal number of people to do the intervention. If this is not the case, we could extend the selection period. Another approach is to add another study centre, an option that does not pose any major challenges as the study is multicentred.

Methodological bias

The study can be an important step to prioritize one weaning protocol over the other. Although the inclusion criteria prevent the generalization of the results to all neonates, it is expected that if the results are satisfactory, a new study could be designed including neonates > 32 weeks of gestation.

It is a clinical trial that studies two different weaning protocols in preterm infants, so it is impossible to be a double-blinded design. To reduce the **detection bias**, the statistical specialist will be blinded to the participants' intervention.

Personal bias

As this is a multicentre trial, there is a potential for **performance bias**. After the child is born, a different neonatologist will attend the newborn, depending on the hospital, the day, and time of birth. This can lead these preterm newborns being treated differently regarding first minute's reanimation, a very important moment for the future outcome. To reduce this performance bias, all professionals participating in the study will receive theoretical training in which they will all be given the same indications.

Another possible limitation, related to the fact that it is a multicentric study, is that the communication between the different hospitals must be flexible and facilitate the identification of any problems.

Confounding bias

There could be confounding factors that could affect the results. In this study, many measures have been taken to reduce this potential bias. Differences between the two groups of the clinical trial are not expected, as randomization will be used. Another preventive measure are the exclusion criteria.

Covariates have also been defined, so a multivariate analysis including these variables will be done. This will allow us to know if some of the differences found between the two groups are directly related to a confounding factor.

12. 2 Strengths

The level of **evidence** in a clinical trial is higher than in an observational study, which is where most of the complications reported in the literature come from.

Due to the nature of the study, an important strength is that **the estimated participant loss is very low**. This can be attributed to the nature of the study, as all preterm newborns on invasive mechanical ventilation require weaning. It can also be attributed to the short follow up period. This avoids or reduces the attrition bias. As it is a multicentre study, a strength is that there is an **increase in external validity**.

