Proposed Criteria for Failure During 2 Hours on CPAP < 5 cmH₂O or T-piece

Clinical Criteria:

- Diaphoresis
- Nasal flaring
- Increasing respiratory effort
- Tachycardia (increase in HR > 40 bpm)
- Cardiac arrhythmias
- Hypotension
- Apnea

Laboratory Criteria:

- Increase of PETCO₂ > 10 mmHg
- Decrease of arterial pH < 7.32
- Decline in arterial pH > 0.07
- PaO₂ < 60mmHg with an FiO₂ > 0.40 (P/F O₂ ratio < 150)
- SpO₂ declines > 5%

Table 3 - Criteria for extubation Readiness Test Failure (56)

Invasive mechanical ventilation in RDS

Despite best efforts to maintain as many preterm babies as possible on NIV, approximately **half of babies < 28 weeks will require invasive mechanical ventilation.** (57)

The aim of invasive mechanical ventilation is to achieve “acceptable” blood gases by ventilating at optimal lung volumes (while avoiding overdistension and atelectasis).

The initial tidal volume is usually set at around 5 ml/kg (58) with a maximum PIP of 25-30 cmH₂O. Adjustments to the initial tidal volume have to be done, according to assessment of work of breathing and blood gas evolution. Required tidal volumes vary around 5-7 ml/kg, the range tending to increase with increasing postnatal age.

PEEP should be adjusted to keep the lung open by finding a point where FiO₂ is at its lowest with haemodynamic stability and acceptable blood gases.

Once stabilised on invasive mechanical ventilation and with evidence of spontaneous respiratory effort, clinicians should immediately start planning for weaning to NIV. Some infants require a very short period of ventilation, particularly those with RDS following surfactant therapy, and early extubation of even the smallest babies who achieve low ventilator settings should be encouraged. (47)

Infant's size, absence of growth restriction, oxygen requirements and blood gases can all help to determine the success of extubation. (59) Delaying extubation does not improve the chances of success.

When weaning from invasive mechanical ventilation, it is reasonable to tolerate a modest degree of hypercarbia, provided the pH remains above 7.22.

Caffeine (20 mg/kg loading, 5-10 mg/kg maintenance) should be used to facilitate weaning from MV.(60)

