7.3 Sampling

7.3.1 Sample size

We estimated the sample size using the free online software GRANMO, and the setting for two independent proportions.

In the view of the literature published so far, the proportion of reintubation in preterm newborns that are on invasive mechanical ventilation is 16% (studies differ between 12% and 20%, an average has been made).(62,63)

Accepting an alpha risk of 0.05 and a beta risk of 0.2 in a two-sided test, **271** subjects are necessary in first group and **271** in the second to recognize as statistically significant a difference greater than or equal to 0.1 percent units. A proportion in one of both groups has been estimated to be 16%. It has been anticipated a drop-out rate of 5% (0,05).

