7.3.3 Estimated time of recruitment

Recruitment will be stratified according to the proportion of preterm newborns in each hospital attends.

According to the last study on the incidence of prematurity stratified by hospital done in Catalonia (64), the 5 hospitals with the highest incidence of extremely and very preterm newborns will be included in the study. They will be named in numbers from 1 to 5.

- Hospital 1 attends 386 extreme and very preterm babies per year
- Hospital 2 attends 333 extreme and very preterm babies per year
- Hospital 3 attends 208 extreme and very preterm babies per year
- Hospital 4 attends 137 extreme and very preterm babies per year
- Hospital 5 attends 106 extreme and very preterm babies per year

The total number of extreme and very preterm babies born in these 5 hospitals per year is 1.170.

The incidence of NRDS in extremely preterm newborns is approximately 70% and the incidence in very preterm newborns is about 50% (6,44,45), so an incidence of 55% have been used to estimate the time of recruitment. (The calculation has been made with the proportion of extremely and very preterm newborns obtained from the last incidence study carried out in Catalonia (6)).

Thus, there are approximately 644 newborns with NRDS per year in these 5 hospitals.

The percentage of preterm infants born at less than 32 weeks' gestation with NRDS requiring invasive mechanical ventilation is 40%, according to the latest report of the Spanish Society of Neonatology (seNeo), carried out in 2021 (61).

So, extrapolating these data, there are 257 neonates with NRDS on invasive mechanical ventilation per year in these 5 hospitals.

To carry out the study, we need a total of 542 participants, 271 for each protocol.

So, **it will take 26 months to obtain the sample (two years and two months).**

The **final stratified recruitment** will be:

- 179 newborns from Hospital 1 (33%)
- 152 newborns from Hospital 2 (28%)
- 97 newborns from Hospital 3 (18%)
- 65 newborns from Hospital 4 (12%)
- 49 newborns from Hospital 5 (9%)

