7.3.4 Randomization and masking

The recruited patients of each hospital will be **randomly divided in two groups**, through an electronic randomization statistical software that will generate a specific identification patient number for the study and will perform a randomization of the patients. The ratio will be 1:1.

Given the nature of the study, it will be a **single blinded trial**, since the newborns do not know which of the two protocols is applied to them.

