8.3 Multivariate interference

It will be necessary to do a multivariate analysis adjusting the covariates according to the independent variable with the dependent variables that can interfere in the results, to avoid possible confusion.

Poisson regression model will be used for the association between the intervention and the number of reintubations, which is a **discrete quantitative variable**.

Cox regression models will be used for the association of the intervention with the **time** of weaning, which is a **continuous quantitative variable**. It is calculated as a survival analysis.

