Annex 7 – Data form

ETIQUETA
IDENTIFICATIVA

DATA FORM

En relació amb el pacient

Setmanes de gestació	
Tipo de preterme	
Per al néixer	
Sexe	
CPR després de néixer	
Apgar score als 5 minuts	

En relació amb la mare

Part preterme previ	
Avortament del segon trimestre	
Edat	
Alçada	
Cirurgia cervical prèvia	
Anomalia uterina congènita	
Diabetis pregestacional	
Malaltia de transmissió sexual	
Fumadora	
Consum alcohol o altres tòxics	
Període intragestacional curt	
Infecció extrauterina	

En relació amb l'embaràs

Embaràs múltiple	
Corioamnionitis	
Ruptura prematura de membranes	
Diabetis gestacional	

En relació amb la intervenció

Codi del protocol utilitzat	
Reintubació	
Temps de weaning (en dies)

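### The adjusted models omit hospital, within which infants are randomised, and the Poisson model carries 21 covariate coefficients on about 57 to 108 events: a near-free gain in precision is left unused

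*Combined protocol and SAP*

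**What the plan says.** **Allocation.** Section 7.3.4 begins "The recruited patients of each hospital will be" and goes on to divide those patients at random into two groups, 1:1. Section 7.3.3 adds "Recruitment will be stratified according to the proportion of preterm newborns in each hospital attends" and gives quotas from 179 infants down to 49. Section 10.3 (Stage 3, item 8) has each centre recruit to its quota at 1:1. Blocking and the form of the allocation list are not described.

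**Adjusted analysis.** Section 8.3 says "It will be necessary to do a multivariate analysis adjusting the covariates according to the independent variable with the dependent variables", limited to covariates that might affect the results. It names Poisson regression for reintubations and Cox regression for weaning time, but lists no covariates and gives no selection rule. Section 12.1, under confounding bias, fills the gap: "Covariates have also been defined, so a multivariate analysis including these variables will be done".

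**Covariates.** Section 7.4 and Table 4 list five neonatal variables (type of preterm, birthweight, sex, CPR, 5-minute Apgar in three bands) and 15 risk factors for prematurity. Hospital appears in neither, nor in sections 8.2 and 8.3, nor among the named fields of Annex 7.

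**Gestational age.** The covariate is a split at 28 weeks, yet Annex 7 has a field for completed weeks, "Setmanes de gestació".

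**Prognosis.** Section 3.3.3 says: "Infant's size, absence of growth restriction, oxygen requirements and blood gases can all help to determine the success of extubation". Of these, the covariate list contains only infant size, as birthweight.

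**The concern.** An adjusted analysis of a randomised trial earns its place by taking up outcome variation that has nothing to do with arm. Two kinds of variable do this: the factor within which allocation is balanced, and baseline variables that predict the outcome. The plan omits the first. It fills the model mostly with variables chosen because they cause early birth, not because they predict failed extubation.

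The plan itself expects centres to differ. Section 12.1 names differences in care by hospital as a source of performance bias, and the training in section 10.3 is meant to reduce differences between centres. If outcomes do vary by hospital, leaving hospital out gives standard errors that do not match the design (usually too wide) and loses some precision.

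Many rare binary covariates set against few events produce empty cells and coefficients that run off to infinity. At stake is the precision and tidiness of the adjusted estimate, not the validity of the trial.

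**Working it through.** **1. The plan's sample size.** Section 7.3.1 gives the error rates ("Accepting an alpha risk of 0.05 and a beta risk of 0.2 in a two-sided test"), one proportion ("A proportion in one of both groups has been estimated to be 16" percent), a difference of 0.1 and 5% drop-out. The unpooled formula is n = (1.960 + 0.842)² × [p₁(1−p₁) + p₂(1−p₂)] / 0.1², divided by 0.95.

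- 16% vs 26%: 7.849 × (0.1344 + 0.1924) / 0.01 = 256.5, so 257; 257 / 0.95 = 270.5, so 271. This matches the plan.
- 16% vs 6%: 7.849 × (0.1344 + 0.0564) / 0.01 = 149.8, so 150; 150 / 0.95 = 157.9, so 158. This does not match.

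The stated 271 fits an increase, while the main hypothesis is a reduction. The direction is not stated, so both ends are carried forward.

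**2. Expected events.** Evaluable infants: 542 × 0.95 = 515. Assume at most one reintubation per infant in 72 hours.

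- 16% vs 6%: 515 × 0.11 = 57
- 16% vs 26%: 515 × 0.21 = 108
- The 12% to 20% literature range in section 7.3.1: 515 × 0.12 = 62 to 515 × 0.20 = 103, inside those limits.

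**3. Coefficients.** Sex 1, type of preterm 1, birthweight 1, CPR 1, Apgar 2, risk factors 15: total 21, or 22 with arm.

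**4. Events per coefficient, Poisson.** 56.65 / 22 = 2.6; 108.15 / 22 = 4.9. Adding four hospital indicators to the full list (26 coefficients) gives 2.2 to 4.2.

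**5. Events per coefficient, Cox.** The event is extubation, which nearly every infant reaches: about 515 / 22 = 23. The overload does not arise there.

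**6. What this does to the arm effect.** I simulated 1,000 trials per scenario: 515 infants, 1:1 within hospital, hospital shares from section 7.3.3. The following are assumptions:

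- 45% extremely preterm;
- binary risk factors at 1% to 30% prevalence;
- outcome effects for preterm group, birthweight, sex and CPR, and none for Apgar or the risk factors;
- hospital log-rate effects from −0.60 to +0.55 (zero in the last row).

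The compact model was arm, preterm group, birthweight and hospital (7 coefficients). Entries are the empirical SD of the arm log rate ratio.

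| Scenario | Events | Full list | Full + hospital | Compact + hospital | Arm only | Full-list fits with a non-finite coefficient |
|---|---|---|---|---|---|---|
| 12% in both arms | 62 | 0.235 | 0.238 | 0.227 | 0.231 | 74% |
| 16% in both arms | 82 | 0.202 | 0.201 | 0.192 | 0.196 | 59% |
| 16%, rate ratio 0.5 | 62 | 0.264 | 0.268 | 0.256 | 0.258 | 73% |
| 16% in both arms, hospitals equal | 82 | 0.200 | 0.201 | 0.193 | 0.199 | 57% |

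- The compact model's SD is 3 to 5% below the full list's (for example 1 − 0.2269/0.2350 = 3.4%; 1 − 0.1915/0.2015 = 5.0%).
- The full list was slightly worse than no adjustment in every row.
- With the full list the mean arm estimate was −0.711 against a true −0.693, and within 0.01 of zero under the null.
- Type I error of the full list with robust errors was 3.5 to 5.0%.
- The compact model had a non-finite coefficient in at most 0.1% of runs.
- In 2 to 7 of each 1,000 runs the full-list calculation could not be completed.
- Adding hospital to the full list brought no gain, so here the benefit came mainly from shortening the list.

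A second simulation with different assumed inputs (1,500 trials per scenario, 514 infants, rate ratio 0.5) gave SDs of 0.264 for the full list and 0.259 for a compact model with hospital, a 2% difference. The Monte Carlo error of a single SD from 1,000 runs is about 1/√2000 = 2.2%. Contrasts within the same simulated trials are tighter than that, but the differences remain small.

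**The case against.** **The arm effect is largely unharmed.** This stands. The diverging coefficients belong to rare nuisance factors, and events per coefficient is a weak guide to the quality of a randomised treatment estimate. A reader might infer from the low ratio that the main adjusted result could not be estimated. The calculations do not support that: the estimate is nearly unbiased and its type I error is close to nominal.

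**The power at stake is small.** A reader might also infer a large loss of power. With the error type held fixed and a rate ratio of 0.5, replacing the list moved power from 80.3% to 81.3% (robust errors) or from 74.1% to 76.6% (ordinary Poisson errors). In the second simulation the moves were 79.9% to 81.3% and 74.1% to 75.6%. Robust errors alone add about 5 to 6 points whatever the covariates, but that is a separate choice and not part of this point.

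**Omitting hospital is normally conservative.** This also stands. When arms are balanced within hospital, ignoring hospital costs some efficiency; it does not inflate false positives.

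**Section 8.3 may intend a selection.** Its wording can be read that way. But no rule is given, section 8.2 tests every covariate against arm, and section 12.1 says the defined variables go in. Under either reading the model is not fixed in advance.

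**Hospital may be recoverable** from the identification label or the shared database. That may be so, but no analysis uses it.

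**Gestational weeks may add little to birthweight**, which is already continuous. The documents do not rank gestational age above other predictors of extubation success, and section 3.3.3 does not name it there. The case for using weeks is only that they are recorded and that the cut discards information.

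**Conclusion.** The point holds as an improvement at almost no cost, not as a threat to validity. Certain from the documents: allocation is 1:1 within hospital; hospital is in neither adjusted model nor in Table 4; the covariate list yields 21 coefficients, 15 of them for risk factors for prematurity; and gestational age is dichotomised although weeks are collected. Following from the plan's own inputs: 57 to 108 events and 2.6 to 4.9 per Poisson coefficient, too few for so long a list whichever direction is meant.

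The size of the loss, about 2 to 5% in the standard error of the arm effect, rests on assumed prevalences and effects. These include no effect of the obstetric factors on reintubation, which favours the short model. The overload does not extend to the Cox model; the omission of hospital does.

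**What to change.** In section 8.3, pre-specify both adjusted models as arm, hospital (five levels; as strata in the Cox model), gestational age in weeks (continuous), birthweight and sex. For Poisson that is 1 + 4 + 1 + 1 + 1 = 8 coefficients, or 56.65 / 8 = 7.1 to 108.15 / 8 = 13.5 events per coefficient. Add hospital to Table 4 and as a named field in Annex 7. Keep the obstetric risk factors for the baseline table only, and bring section 12.1 into line.

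The cost is a few lines of text and one form field. Weeks, birthweight and sex are already on the form, so no new measurement is needed.

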13. IMPACT

Newborn respiratory distress syndrome (NRDS) is the most common complication of prematurity.

The incidence of prematurity has increased over the last 50 years due to a surge in the number of established preterm births. Accordingly, the increasing number of preterm births has led to an increase in associated complications. As a result, NRDS has become more relevant in preterm infants.

Despite reductions in mortality rates, the incidence of complications and morbidity in these infants remains high, particularly in those requiring invasive mechanical ventilation, the most severe cases. Minimising the duration of this type of ventilation is essential to reduce the risk of complications, morbidity and mortality, and studies have shown that reducing the duration significantly reduces these risks.

Therefore, finding a weaning protocol that minimises the frequency of reintubations and the overall duration of weaning may reduce the associated complications and reduce morbidity and mortality from both the syndrome and mechanical ventilation.

Therefore, this research has been carried out because premature babies are an extremely vulnerable group, for whom improvements in medical care can have a significant impact on their wellbeing, both in the immediately and in the longer term.

Reducing the duration of intubation and the number of reintubations not only benefits the newborn, but also has a positive impact on the families of patients, who usually experience significant suffering during the time the baby is in the NICU, and especially while intubated.

14. FEASIBILITY

This clinical trial will take place in five hospitals, each equipped with a NICU and experienced in the treatment of preterm babies. The participation of these centres will allow the required sample size of 542 patients to be achieved within two years and two months, which is not considered a long time.

Weaning is necessary for a posterior extubation. Therefore, it is believed that parents or legal guardians will not hesitate to participate in the study, as there is no additional risk to the newborns.

The professional neonatal team of each hospital, who will be responsible for carrying out the intervention and subsequent follow-up, will be trained in the management of intubated newborns. So, they will be perfectly capable of developing the intervention of the study.

The study budget is not excessive as the necessary intervention equipment is already available in the participating hospitals. Moreover, no additional personnel will be needed except for the statistical expert, the data manager and the computer scientist.

In conclusion, this study is feasible.

16. ANNEXES

Annex 1 – APGAR score

Sign	0 points	1 point	2 points
Activity (muscle tone)	Floppy	Some tone and flexion	Active movement
Heart rate	Absent	<100 bpm	>100 bpm
Grimace (reflex irritability)	Absent	Minimal response to stimulation	Prompt response to stimulation (sneeze cough pull away)
Appearance	Blue or pale	Pink body, blue extremities	Completely pink
Respiration	Absent	Slow and irregular	Vigorous cry

Severely depressed	0-3
Moderately depressed	4-6
Excellent condition	7-10

Annex 2 - Diagnosis, signs and symptoms and treatment of NEC

Diagnosis	Signs and symptoms	Treatment strategy
Suspected NEC	Abdominal distension without radiographic evidence of pneumatosis intestinalis, portal venous gas, or free intraperitoneal air	Close clinical observation for increased abdominal distention and feeding intolerance
	Unexpected onset of feeding intolerance	Consideration of bowel decompression and brief discontinuation of feeding; abdominal radiograph; monitoring of white cell, differential, and platelet counts; consideration of blood cultures and short course of intravenous antibiotics
Definitive medial NEC	Abdominal distension with pneumatosis intestinalis, portal venous gas, or both	Bowel decompression and cessation of enteral nutrition for 7-10 days
	Other radiographic signs such as fixed, dilated bowel loops of intestine and ileus patterns are not pathognomonic but should be treated as such	Close monitoring of white cell, differential and platelet counts, blood culture and intravenous antibiotics for 7-10 days, close monitoring of abdominal radiographs, notification of surgical team
Surgical NEC	Free intraperitoneal air on abdominal radiograph after initial medical signs and symptoms	Exploratory laparotomy with resection if necessary
	Persistent ileus pattern, abdominal distention, and radiographs showing absence of bowel gas, coupled with worsening clinical and laboratory values	Placement of drain

